6.4. Study Treatment Compliance

Patient compliance with study treatment will be assessed at each visit. Compliance with all study-related treatments should be emphasized to the patient by the site personnel, and appropriate steps should be taken to optimize compliance during the study. Compliance will be assessed by an accounting of returned study drugs (tablet/capsule counts) and patient interviews. Patients will be instructed to bring all study drugs (used, partially used, unused drug and/or empty containers) with them to study site visits in order for site personnel to

assess study drug accountability. Deviation(s) from the prescribed dosage regimen should be recorded in source and in the eCRF.

6.5. Concomitant Therapy

All concomitant medications and treatments (including over-the-counter or prescription medicines, vitamins, vaccines and/or herbal supplements) must be recorded in the eCRF. Details regarding **all** prior anticancer treatments will also be recorded in the eCRF.

Any prior medication received up to 28 days before the first dose of study treatment and 30 days after the last dose of study treatment, or until the patient begins a new anticancer therapy, whichever occurs first will be recorded in the eCRF. Any addition, deletion or change in the dose of these medications will also be recorded. Unless specifically prohibited, concomitant medications can be administered at the Investigator's discretion to manage the patient's medical condition.

All concomitant treatments/procedures (including over-the-counter or prescription medications, vitamins and/or herbal supplements) that are required to manage a patient's medical condition during the study will be recorded in the eCRF including:

- Reason for use.
- Dates of administration including start and end dates.
- Dosage information (using generic drug names when possible), including dose and frequency.

COVID-19 vaccines approved under an EUA (or equivalent) are considered allowed concomitant medications and standard AE collection and reporting processes should be followed. The timing of vaccine dosing relative to the dosing of study medications is at the discretion of the investigator although administration should be avoided on the first day of study medication dosing.

The Sponsor should be contacted if there are any questions regarding concomitant or prior therapy.

6.5.1. Permitted Concomitant Therapy Requiring Caution and/or Action

6.5.1.1. CYP and UGT Substrates and Inhibitors

Encorafenib is a reversible inhibitor of CYP2B6, CYP2C9, CYP3A4 and UGT1A1. It is also a time-dependent inhibitor of CYP3A4, and induced CYP2B6, CYP2C9 and CYP3A4 in human primary hepatocytes. Permitted medications to be used with caution in this study include those that are sensitive substrates of CYP2B6, CYP2C9, CYP3A4 and UGT1A1 or those substrates that have a narrow therapeutic index.

There is a potential for encorafenib to induce CYP3A4, which may reduce the effectiveness of hormonal contraception methods. Therefore, the use of at least 1 form

of non-hormonal contraception is required for females of childbearing potential during participation in this study.

Caution should be used in patients receiving concomitant treatment with other drugs that are substrates of CYP3A4 as the efficacy of these drugs could be reduced when administered with encorafenib.

Encorafenib has been identified to be metabolized by CYP3A4 and to a lesser extent by CYP2C19 in vitro. **Concomitant use of moderate CYP3A4 inhibitors should be avoided.** If use of a moderate CYP3A4 inhibitor is unavoidable, short-term use (\leq 30 days) following discussion with the Sponsor may be permitted with an accompanying dose reduction to one-half of the encorafenib dose prior to use of the moderate CYP3A4 inhibitor. After the inhibitor has been discontinued for 3 to 5 elimination half-lives, resume the encorafenib dose that was taken prior to initiating the CYP3A4 inhibitor.

In vitro, binimetinib has been identified to be primarily metabolized by glucuronidation. Strong inducers of UGT1A1 should be taken with caution when co-administered with binimetinib.

For tabulated CYP substrates, inhibitors and inducers to be used with caution or avoided, please consult with the FDA website: Drug Development and Drug Interactions: Table of Substrates, Inhibitors and Inducers.

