6.1. Study Treatments Administered

6.1.1. Encorafenib

Encorafenib will be self-administered orally without regard to food. Encorafenib should be taken daily in the morning at approximately the same time (± 2 hours) every day. Patients should be directed to take encorafenib and binimetinib together as applicable. Patients will swallow the study intervention whole, and will not manipulate by, for example, opening or crushing, or chew the study intervention. If a patient vomits at any time after dosing, the dose should not be re-administered. Doses of encorafenib that are omitted for AEs or any other reason should not be made up during the day, or at the end of the dosing period. Additional information regarding encorafenib administration is provided in the IPM.

Encorafenib will begin on Cycle 1 Day 1 and will be self-administered continuously, except on study visit days (e.g., Day 1 of each cycle; see Table 3), and days when PK samples will be drawn (see Table 12 and Table 13), when the encorafenib dose will be administered at the study site under observation of the Investigator. Treatment may continue if the patient has not met any of the protocol-defined conditions for treatment withdrawal (see Section 6.7).

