6.1.2. Binimetinib

Binimetinib will be self-administered orally without regard to food. Binimetinib should be taken 12 ± 2 hours apart in the morning and in the evening at approximately the same times every day. Patients should be directed to take binimetinib and encorafenib together as applicable. Patients will swallow the study intervention whole, and will not manipulate by, for example, opening or crushing, or chew the study intervention. If a patient vomits at any time after dosing, the dose should not be re-administered, and the patient should take the next scheduled dose. Doses of binimetinib that are omitted for AEs or any other reason should not be made up during the day, or at the end of the dosing period. Additional information regarding binimetinib administration is provided in the IPM.

Binimetinib will begin on Cycle 1 Day 1 and will be self-administered continuously, except on study visit days (e.g., Day 1 of each cycle; see Table 3), and days when PK samples will be drawn (see Table 12 and Table 13), when the morning binimetinib dose will be administered at the study site under observation of the Investigator. Treatment may continue if the patient has not met any of the protocol-defined conditions for treatment withdrawal (see Section 6.7).

| Study Treatment Name | Encorafenib | Binimetinib |
|----------------------|-------------|-------------|
| Туре | Drug | Drug |

Table 6.Study Treatments

| Study Treatment Name | Encorafenib | Binimetinib |
|-------------------------|--|--|
| Dose Formulation | Capsule | Tablet |
| Unit Dose Strength | 75 mg | 15 mg |
| Dosage Levels | 450 mg QD | 45 mg BID |
| Route of Administration | Oral | Oral |
| Sourcing | Encorafenib will be provided centrally by the Sponsor or designee | Binimetinib will be provided centrally by the Sponsor or designee |
| Packaging and Labeling | Encorafenib will be provided in high-density polyethylene bottles. Each bottle will be labeled per local regulatory requirements. | Binimetinib will be provided in high-density polyethylene bottles. Each bottle will be labeled per local regulatory requirements. |
| Former Names or Aliases | LGX818 ONO-7702 W0090 | ARRAY-438162 MEK162 ONO-7703 W0074 |

Table 6.Study Treatments

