6.6.2. Dose Modifications

Doses of encorafenib and binimetinib may be independently reduced for toxicity management as outlined in Table 7 and Table 8, respectively. All dose modifications are based on the worst preceding toxicity. The treating Investigator should refer to and follow the labeled guidance and/or institutional guidelines for the management of toxicities relating to encorafenib and binimetinib. Detailed guidelines can also be found in Appendix 2 and Appendix 3.

When the AE that resulted in a dose reduction improves to and remains stable to the patient's baseline for a minimum of 14 days, the dose can be re-escalated to the next higher dose level at the discretion of the Investigator, provided there are no other concomitant toxicities that would prevent drug re-escalation. There is no limit to the number of times the patient can have their dose reduced or re escalated; however:

- No dose re-escalation of encorafenib is allowed after a dose reduction due to prolonged $QTcF \ge 501$ msec
- No dose re-escalation of binimetinib is allowed after a dose reduction due to LVEF dysfunction
- No dose re-escalation of binimetinib or encorafenib is allowed after a dose reduction due to ocular toxicity ≥ Grade 2

| Dose Level | Encorafenib |
|-------------------|------------------------|
| 0 (starting dose) | 450 mg QD |
| -1 | 300 mg QD |
| -2 | 225 mg ^a QD |

| Table 7. | Dose | Reductions | for | Encorafenib |
|----------|------|------------|-----|-------------|
|----------|------|------------|-----|-------------|

NOTE: Dose reduction should be based on the highest AE grade.

a Dose reduction below 225 mg QD of encorafenib is not allowed.

Table 8. **Dose Reductions for Binimetinib**

| Dose Level | Binimetinib |
|-------------------|------------------------|
| 0 (starting dose) | 45 mg BID |
| -1 | 30 mg ^a BID |

NOTE: Dose reduction should be based on the highest AE grade.

a Dose reduction below 30 mg BID of binimetinib is not allowed.

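### Protocol 6.5.1.1: the half-dose condition for a moderate CYP3A4 inhibitor cannot be carried out in a patient taking encorafenib 225 mg QD

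*Protocol*

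**What the plan says.** **Interaction rule.** Protocol 6.5.1.1 sets avoidance as the default: "Concomitant use of moderate CYP3A4 inhibitors should be avoided". For unavoidable use of up to 30 days, the exception reads "following discussion with the Sponsor may be permitted with an accompanying dose reduction to one-half", the full condition being a "dose reduction to one-half of the encorafenib dose prior to use of the moderate CYP3A4 inhibitor". The earlier dose is resumed once the inhibitor has been stopped for 3 to 5 elimination half-lives. The section makes no exception by dose level and gives no rounding rule.

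**Supply and administration.** Table 6 gives "Unit Dose Strength | 75 mg | 15 mg"; the first figure is the encorafenib capsule and the second the binimetinib tablet. Section 6.1.1 has encorafenib taken every day and adds: "Patients will swallow the study intervention whole, and will not manipulate by, for example, opening or crushing".

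**Dose levels.** Table 7 in Section 6.6.2 lists 450, 300 and 225 mg QD. Its footnote says "Dose reduction below 225 mg QD of encorafenib is not allowed". The table is introduced with "Doses of encorafenib and binimetinib may be independently reduced for toxicity management as outlined in Table 7 and Table 8, respectively", and its note says "Dose reduction should be based on the highest AE grade".

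**Interruptions.** Section 6.6.1 lets dosing be paused for medical, surgical or logistical reasons unrelated to study treatment. The return default is 14 days unless otherwise discussed with the Sponsor. Encorafenib stops permanently after more than 42 consecutive missed days. CYP3A4 inhibitors are not named there, and Sections 6.5.1.1, 6.6.1 and 6.6.2 do not refer to one another on this point.

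**The concern.** A dosing instruction that applies at every level should work at every level, or say where it does not apply. Here the lowest level gives a half-dose that cannot be made up from whole capsules.

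The protocol's own tables lead patients to 225 mg. In Appendix 2, a first or second Grade 3 hand-foot skin reaction is followed by restarting one level lower, so two such events take a patient from 450 to 300 to 225 mg. The QTc entries also step down one level at each of two occurrences, and Section 6.6.2 bars re-escalation after a reduction for QTcF of 501 msec or more. These patients have already been reduced for toxicity, and Section 6.5.2 shows that raised encorafenib exposure under CYP3A4 inhibition is a recognised concern. A site facing an unavoidable inhibitor in such a patient would find the one dosing condition written for permitted use impossible to follow.

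**Working it through.** **Inputs**
- Capsule strength: 75 mg (Table 6).
- Dose levels: 450, 300 and 225 mg QD (Table 7).
- Interaction rule: one-half of the prior dose (6.5.1.1).
- Footnote floor: 225 mg QD (Table 7).
- Capsules swallowed whole (6.1.1).

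**Reproducing the plan's figure.** Table 2 states the starting dose as 6 capsules of 75 mg. 6 × 75 = 450 mg, which agrees.

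**Check.** Half-dose = dose / 2; capsules = half-dose / 75.

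| Level before inhibitor | Half-dose | Capsules | Whole number? | At or above 225 mg? |
|---|---|---|---|---|
| 450 mg | 225 mg | 225 / 75 = 3.0 | yes | yes |
| 300 mg | 150 mg | 150 / 75 = 2.0 | yes | no |
| 225 mg | 112.5 mg | 112.5 / 75 = 1.5 | no | no |

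**Two readings of the floor**
- If it covers toxicity reductions only, 300 mg can be halved with whole capsules, and only the halving of 225 mg fails.
- If it covers all reductions, halving 300 mg is barred too, and only the 450 mg level satisfies both sections.

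The failure at 225 mg does not depend on the reading, because it rests on the capsule count.

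**Interruption route.** Against the 14-day return default, a 30-day inhibitor course is 30 − 14 = 16 days longer, so the Sponsor would have to agree a later return. Against the 42-day limit it leaves 42 − 30 = 12 days, from which the 3 to 5 half-lives would come if dosing stayed paused for that time too. That period depends on the inhibitor.

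**Reach.** The documents give no rate for patients at 225 mg and none for need of a moderate inhibitor, so no count can be derived. One route can be bounded under an assumption: if the 0.5% rate of QTcF above 500 ms reported from the melanoma trial (Protocol 2.1.4) held here, 107 × 0.005 = 0.535 patients would be expected to have any such event, and fewer would go through two reductions. This bound does not cover hand-foot skin reaction or other toxicities.

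**The case against.** The strongest reply is that this is a gap in a permission, not a clash of obligations. Avoidance is the default, and the Sponsor is consulted before any half-dose is given. If the condition cannot be met at 225 mg, the permission can be taken as unavailable and the default stands. Nothing obliges a site to dispense 1.5 capsules. That stands, and it keeps the point small. It does not make the written condition workable, and the text does not say that the permission lapses at 225 mg.

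Three stronger readings are tempting but not supported:

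- **That any Sponsor-agreed alternative would breach the protocol.** Section 6.6.1 permits interruptions for unrelated medical events, gives its examples as illustrations, and lets the return time be discussed with the Sponsor. An illness that makes an inhibitor unavoidable may fall within it, so a written route may exist. The sentence refusing waivers opens Section 7, on visits and assessments. The Section 9.2 refusal to pre-authorize deviations matters only if the action is a deviation.
- **That the 300 mg level contradicts Table 7.** The table is introduced for toxicity management, its note refers to AE grade, and Section 6.7 ties it to toxicity. The scope of the floor is unclear, which is less than a contradiction.
- **That 225 mg is itself unworkable.** It is three whole capsules; only halving it fails.

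Two further points stand. The route to 225 mg is not equally firm everywhere: in the text available, the second-occurrence QTc entry is followed by an unlabelled line on permanent discontinuation, possibly a lost row label, and re-escalation remains possible after a hand-foot reduction. The Investigational Product Manual and Pharmacy Manual, to which the protocol defers for administration and handling detail, were not available and might address this.

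**Conclusion.** The point holds, as a minor one. On the protocol's own figures, the half-dose condition in Section 6.5.1.1 cannot be carried out for a patient on 225 mg QD: it needs 1.5 capsules that must be taken whole. This rests on 75 mg being the only encorafenib strength supplied, as Table 6 lists, and on the half-dose rule applying at every level, as written. Confidence in it is high.

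Whether the Table 7 floor also governs interaction-driven reductions is an open question. The 300 mg level is affected only if it does.

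Few patients are likely to meet the combination of a twice-reduced dose and an unavoidable moderate inhibitor, although the documents do not allow a count. The endpoint, sample size and ORR analysis do not change.

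**What to change.** Reconcile Section 6.5.1.1 with Section 6.1.1, Table 6, Section 6.6.1 and Section 6.6.2 with Table 7, so that at each Table 7 level the half-dose instruction is either executable or expressly unavailable. State whether the Table 7 floor covers reductions made for a drug interaction, and cross-refer the sections, including whether Section 6.6.1 applies when an inhibitor is needed. Check that the two product manuals agree. The sponsor's clinical team decides the rule; none is proposed here.

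The cost is one or two sentences in a protocol clarification or administrative letter, with no change to the SAP or to any analysis.

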6.5.1.2. Transporter Substrates and Inhibitors

In vitro data showed that encorafenib is a substrate of the transporter P-gp. Thus, drugs that are known to inhibit or induce P-gp should be used with caution. Encorafenib is also a potent inhibitor of the renal transporters, OAT1, OAT3 and OCT2, and the hepatic transporters OATP1B1 and OATP1B3. The co-administration of drugs that are known to be sensitive or narrow therapeutic index substrates of OAT1, OAT3, OCT2, OATP1B1 or OATP1B3 should be used with caution.

Binimetinib has also been shown to be a substrate of P-gp and BCRP. It is advised that inhibitors and inducers of P-gp and BCRP transporters should be taken with caution when co-administered with binimetinib.

For tabulated transporter substrates, inhibitors and inducers to be used with caution, please consult with the FDA website: Drug Development and Drug Interactions: Table of Substrates, Inhibitors and Inducers.

6.5.1.3. Drugs with a Conditional or Possible Risk to Prolong QT Interval and/or Induce Torsade de Pointes

Investigators should use caution when administering encorafenib with concomitant medications with a known, conditional or possible risk to prolong the QT interval and/or induce torsade de pointes. Patients receiving such medications must be carefully monitored for potentiating of toxicity due to any individual concomitant medication and may require dose titration of the concomitant medication. See the CredibleMeds® website: Combined List of Drugs That Prolong QT and/or cause Torsades de Pointes (TDP).

6.5.2. Prohibited Concomitant Therapy

Medications specifically outlined below are not allowed during the study. If there is a clinical indication for one of these medications specifically prohibited during the study, discontinuation from the study treatment may be required. Patients may receive other medications that the Investigator deems to be medically necessary. The Investigator should discuss any questions regarding medications with the Sponsor. The final decision on any supportive therapy rests with the Investigator and/or the patient's primary physician. The decision to continue the patient in the study requires mutual agreement of the Investigator, the Sponsor and the patient.

The following therapies are prohibited during the Screening and Treatment Periods of this study (unless otherwise noted). There are no prohibited therapies during the post-treatment Follow-up Period.

- No additional anticancer agents such as cytotoxic chemotherapy, small-molecule targeted agents, biological agents, immune response modifiers or hormonal therapy are to be administered to patients while they are receiving study treatment.
- Investigational drugs and devices.
- Radiation therapy (not including palliative radiotherapy at focal sites that covers ≤ 10% of the bone marrow reserve).
 Note: The patient must have clear measurable disease outside the radiated field.
 Note: Radiation therapy to a symptomatic solitary lesion or to the brain may be considered on a case-by-case basis after consultation with the Sponsor. *Note:* Administration of palliative radiation therapy will be considered clinical progression for the purposes of determining PFS.
- Concomitant strong systemic CYP3A4 inhibitors, which could significantly increase the exposure of encorafenib.
- Concomitant moderate or strong systemic CYP3A4 inducers, which could significantly decrease the exposure of encorafenib.

6.6. Dose Modification

6.6.1. Dose Interruptions

Following initiation of therapy, treatment with encorafenib and binimetinib may be delayed to allow resolution of toxicity. Patients may resume treatment if no medical condition or other circumstance exists that, in the opinion of the Investigator, would make the patient unsuitable for further participation in the study.

Individual decisions regarding dose interruptions and modifications should be made using appropriate clinical judgment, considering relatedness of the AE to the study treatment and the patient's underlying condition. Adverse events that have a clear alternative explanation, or transient (\leq 72 hours) abnormal laboratory values without associated clinically significant signs or symptoms may be exempt from dose-reduction rules. The treating Investigator

should refer to and follow the labeled guidance and/or institutional guidelines for the management of toxicities relating to encorafenib and binimetinib. Detailed guidelines can also be found in Appendix 2 and Appendix 3.

Dose interruptions are permitted in the case of medical/surgical events or logistical reasons not related to study treatment (e.g., elective surgery, unrelated medical events, vacation, holidays). Patients should be placed back on study treatment within 2 weeks (14 days) of the scheduled interruption, unless otherwise discussed with the Sponsor. The reason for interruption will be documented in the patient's study record.

If a patient misses > 6 weeks (i.e., 42 consecutive days) of dosing with encorafenib, study treatment with encorafenib will be permanently discontinued. Due to the potential for limited efficacy of binimetinib alone in the study population, if a patient permanently discontinues treatment with encorafenib, they must also permanently discontinue treatment with binimetinib.

If a patient misses > 6 weeks (i.e., 42 consecutive days) of dosing with binimetinib, study treatment with binimetinib will be permanently discontinued. If a patient discontinues treatment with binimetinib, the patient may continue treatment with encorafenib. Due to the potential for increased toxicity when binimetinib is discontinued, doses of single-agent encorafenib may need to be decreased.

